9.4.6 Response Review

For trials where the response rate is the primary endpoint, all responses will be reviewed by an expert independent of the study at the study's completion. Simultaneous review of the patients' files and radiological images is the best approach.

10.0 DATA AND SAFETY MONITORING

In compliance with the Washington University Institutional Data and Safety Monitoring Plan, the Principal Investigator will provide a Data and Safety Monitoring (DSM) report to the Washington University Quality Assurance and Safety Monitoring Committee (QASMC) semi-annually beginning six months after accrual has opened (if at least five patients have been enrolled) or one year after accrual has opened (if fewer than five patients have been enrolled at the six-month mark).

The Principal Investigator will review all patient data at least every six months, and provide a semi-annual report to the QASMC. This report will include:

- HRPO protocol number, protocol title, Principal Investigator name, data coordinator name, regulatory coordinator name, and statistician
- Date of initial HRPO approval, date of most recent consent HRPO approval/revision, date of HRPO expiration, date of most recent QA audit, study status, and phase of study
- History of study including summary of substantive amendments; summary of accrual suspensions including start/stop dates and reason; and summary of protocol exceptions, error, or breach of confidentiality including start/stop dates and reason
- Study-wide target accrual and study-wide actual accrual
- Protocol activation date
- Average rate of accrual observed in year 1, year 2, and subsequent years
- Expected accrual end date
- Objectives of protocol with supporting data and list the number of participants who have met each objective
- Measures of efficacy
- Early stopping rules with supporting data and list the number of participants who have met the early stopping rules
- Summary of toxicities
- Abstract submissions/publications
- Summary of any recent literature that may affect the safety or ethics of the study

The study principal investigator and Research Patient Coordinator will monitor for serious toxicities on an ongoing basis. Once the principal investigator or Research Patient Coordinator becomes aware of an adverse event, the AE will be reported to the HRPO and QASMC according to institutional guidelines.

11.0 STATISTICAL CONSIDERATIONS

11.1 Power

Our power analysis is based on the following hypotheses. The null hypothesis assumes that the 3-month progression-free survival (PFS) for treatment with ablation therapy is

overall 20% for patients with metastatic sarcoma. We hypothesize in the alternative hypothesis that the 3-month PFS will be at least 40% with ablation therapy. This is based on data from a clinical trials database used to provide reference values for conducting phase II studies in sarcoma with PFR as the principal endpoint (5). An enrollment of 36 patients can achieve at least 80% power to conclude that the alternative hypothesis is true based on a two-sided test of one-sample proportion at a significance level of 0.05.

11.2 Data Analysis

Possible covariates in the analysis include sex, age, number of lesions and total diameter of all ablated lesions. Descriptive statistics (mean, median, range and standard deviation) will be provided for continuous variables and frequencies will be tabulated for categorical variables for the patients. Kaplan-Meier survival estimates will be obtained for 3-month PFS for patients with ablation therapy. For categorical covariates such as sex, number of lesions (<5 vs. ≥5) and total diameter of all ablated lesions (10cm vs. ≥10cm), if there are sufficient number of patients in each stratum, Kaplan-Meier survival curves will be plotted for each stratum and log-rank test will be performed to test if 3-month PFS is significantly different across strata. Overall survival will be analyzed with the same strategy as for 3-month PFS.

To determine whether or not there is an improvement in quality of life (QOL), since the variables related to QOL are in ordinal scale and will be measured at baseline, one day post ablation, one month post ablation and at time of disease progression, the GEE analysis implemented in SAS PROC GENMOD will be used to take into account the correlation of repeated measures from the same subject. Contrast statements will be used to compare mean QOL scores between any two times. The same analysis strategy will be performed to determine if BPI changes over time.

All analyses will be two-sided at a significance level of 0.05 and will be performed with statistical software SAS 9.3.

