3.0 PATIENT SELECTION

3.1 Inclusion Criteria

1. Histologically or cytologically confirmed high-grade metastatic sarcoma that has been stable on 6-12 cycles of one chemotherapeutic regimen (cytotoxic or biologic) although a change in chemotherapy is allowed if it is a result of toxicity/tolerability rather than progression. A patient must not have evidence of progression at any time while on chemotherapy in order to be eligible for this trial.
2. Measurable disease defined as lesions that can be accurately measured in at least one dimension (longest diameter to be recorded) as ≥ 10 mm with CT scan, PET CT, or MRI exam.
3. At least 18 years of age.
4. ECOG performance status ≤ 2 (Karnofsky $\geq 60\%$, see Appendix A)
5. Normal bone marrow and organ function as defined below:
 - a. Leukocytes $\geq 3,000/\text{mcl}$
 - b. Absolute neutrophil count $\geq 1,500/\text{mcl}$
 - c. Platelets $\geq 100,000/\text{mcl}$
 - d. Total bilirubin $\leq 1.5 \times \text{IULN}$ or $3 \times \text{IULN}$ with normal ALT and AST in patients with Gilbert's disease
 - e. $\text{AST(SGOT)/ALT(SGPT)} \leq 3.0 \times \text{IULN}$

- f. Creatinine less than the institutional upper limit of normal
OR
Creatinine clearance ≥ 50 mL/min/1.73 m²
 - g. INR < 1.5 or patient off Coumadin at the time of ablation
6. No more than 10 treatable lesions as evaluated by an experienced interventional oncologic radiologist for eligibility and lesion accessibility as the ablation of more than 10 lesions becomes technically infeasible. These lesions must be treated in a two- to three-week time period from initial interventional radiology evaluation. Lung and liver lesions can range from 1 cm to 7 cm for a single lesion and no greater than 5 cm for multiple lesions. There are no size criteria for the osseous lesions.
 7. The lesions will be amenable to a safe, ultrasound/computed tomographic/fluoroscopic guided percutaneous approach. The targeted metastases must be sufficiently separateable from the central nervous system, major peripheral motor nerves, bowel, and bladder. All lesions must be amenable to treatment.
 8. If patients have received radiation therapy, there must be a one-month washout period.

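### Section 11.2 tests lesion number and total ablated diameter only as two-way splits and specifies no test or model for age, so the exploratory PFS and OS covariate analyses lose information

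*Combined protocol and SAP*

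**What the plan says.** All of the covariate plan is in section 11.2 of the combined protocol and SAP.

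- Four candidates are named: "Possible covariates in the analysis include sex, age, number of lesions and total diameter of all ablated lesions".
- Two quantitative ones are handled as binary: "number of lesions (<5 vs. ≥5) and total diameter of all ablated lesions (10cm vs. ≥10cm". (The less-than sign missing before the first 10 cm may have been lost in text extraction and is not counted as an error.)
- The method is a set of curves by stratum, after which a "log-rank test will be performed to test if 3-month PFS is significantly different across strata". It applies only "if there are sufficient number of patients in each stratum". No number is attached to that condition.
- Overall survival inherits the approach: "Overall survival will be analyzed with the same strategy as for 3-month PFS".
- For continuous variables the plan offers summaries: "Descriptive statistics (mean, median, range and standard deviation) will be provided for continuous variables". No Cox, logistic or other model with a continuous covariate is named for PFS or OS. Age has no cut-point, test or model.

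Section 3.1 sets the range that the cut-points divide: "No more than 10 treatable lesions as evaluated by an experienced interventional oncologic radiologist". Lung and liver lesions may measure 1 to 7 cm if single and up to 5 cm if multiple; osseous lesions have no size limit.

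**The concern.** Splitting lesion count at 5 treats patients with 4 and 5 lesions as different, and patients with 5 and 10 as the same. Total diameter has a wider range: for lung and liver lesions alone, section 3.1 allows from 1 cm up to 10 × 5 = 50 cm, and a single cut at 10 cm puts most of that range in one group. The documents give no reason for either cut.

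The sufficiency condition adds a second loss. With 36 patients, an uneven split could remove a covariate from testing altogether, on a judgement that has no stated threshold and could be made after the data are seen. A continuous term needs no such condition. Age is named as a candidate, but any analysis of it would have to be devised later.

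At stake is how much these exploratory analyses can say about prognosis from a small number of events.

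**Working it through.** **1. The plan's own figure, and whether covariates enter it.** Section 11.1 gives 36 patients for 20% against 40%, two-sided 0.05, at least 80% power. The normal-approximation formula gives

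n = [(1.96·√(0.2·0.8) + 0.8416·√(0.4·0.6)) / 0.2]² = [(0.7840 + 0.4123) / 0.2]² = 35.8, rounded up to 36.

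The figure reproduces. It is an unadjusted one-sample proportion test, so nothing below touches it. The documents state no figure for information lost by splitting a covariate.

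**2. Normal covariate, effect linear on the log-hazard (assumption).** The share of information kept by a binary split is the squared correlation between the covariate and its split. For a cut at quantile q with normal deviate z this is φ(z)² / [q(1−q)].

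- Median: 0.3989² / 0.25 = 0.637 kept, 36% lost.
- 25/75: 0.3178² / 0.1875 = 0.539 kept, 46% lost.
- The same formula gives losses of 42% at 30/70, 51% at 20/80 and 66% at 10/90.

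**3. Other assumed distributions.** Lesion count is an integer capped at 10, so normality is doubtful. For counts uniform on 1 to 10, the variance is 8.25. The groups below 5 and from 5 up have means 2.5 and 7.5 and shares 0.4 and 0.6. The between-group variance is 0.4 × 0.6 × 5² = 6, so 6 / 8.25 = 73% is kept and 27% lost. Further cases:

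| Covariate and assumed shape | Information lost |
|---|---|
| Count, U-shaped (54% at 5 or more) | 13% |
| Count, uniform | 27% |
| Count, truncated geometric | 26–47% |
| Count, truncated Poisson | 33–75% |
| Total diameter, lognormal, median 5–15 cm | 34–80% |

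The upper ends come from very uneven splits. The 80% case has about 4% of patients above 10 cm, or 0.042 × 36 = 1.5 patients, and the 75% case has about 2% with 5 or more lesions. There the sufficiency condition would probably drop the test rather than run it weakly.

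**4. What this means in events.** Information on PFS or OS comes from events. If the plan's alternative holds, 60% of 36 = 21.6, or about 22, have progressed by 3 months; under its null, 80% of 36 = 28.8, or about 29. With D events and share kept r, approximate power for a hazard ratio HR per standard deviation is Φ(√(D·r)·ln HR − 1.96). The hazard ratios are assumed.

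| D | HR per SD | Continuous | Median split | 20/80 split |
|---|---|---|---|---|
| 22 | 1.4 | 35% | 24% | 20% |
| 22 | 1.5 | 48% | 33% | 26% |
| 22 | 1.75 | 75% | 55% | 45% |
| 29 | 1.75 | 85% | 67% | 56% |

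At 22 events, a median split leaves the information of 22 × 0.637 = 14 events, and a 25/75 split that of 22 × 0.539 = 12.

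**5. The planned log-rank tests as they stand.** By the Schoenfeld formula, 80% power for a between-group hazard ratio of 2 needs 7.849 / [q(1−q)·(ln 2)²] events: 66 at 50/50 and 103 at 20/80. Both exceed the 36 patients. With 22 events the power is about 37% and 26%.

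**The case against.** The strongest reply is that little depends on this. The objectives in sections 2.1 and 2.2 are progression-free rate, survival, quality of life and pain; none is prognostic. The covariates are only called possible ones. That stands, and it makes this a cheap improvement rather than a threat to the trial. A reader might infer that the main result of a 36-patient trial loses a third of its information. Step 1 shows it loses none.

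Four further points also stand.

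- Lesion count and diameter are tempting to read as showing who benefits from ablation. Section 1.2 describes a single-arm trial. Without a control group, neither a log-rank test nor a Cox model can separate benefit from prognosis.
- A loss of at least a third might be inferred from the normal-covariate result. It is not a floor: several plausible count distributions give 13% to 30%. If the true effect is a step near the cut, the split is the better model.
- Age is not wholly without analysis. It falls under the descriptive statistics, and "For categorical covariates such as sex, number of lesions (<5 vs. ≥5" leaves the list of categorical covariates open, so age could be grouped. What is missing is any specified test or model relating it to outcome.
- The gain is modest for modest effects (35% against 24% at a hazard ratio of 1.4), and pre-specified cut-points do avoid data-driven ones.

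It might also be objected that exact total diameter is not certain to be recorded, since section 9.2 requires measurements of at most five target lesions. The planned 10 cm split needs the same sizes, so this does not favour the present plan.

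**Conclusion.** The point holds as a minor one. The plan's only method for relating quantitative covariates to PFS and OS is a split at a fixed cut, subject to an undefined sufficiency condition, and age has no specified association analysis.

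If effects are near linear, the loss is about 36% at a median split and 46% at 25/75 for a normal covariate, and about 13% to 80% over the other shapes tried. None of these is a document figure. It would be wrong to read the result as 36 patients acting like 23, because for PFS and OS the loss applies to whatever number of events occurs. The analyses remain weak and exploratory under either method, which is a reason not to give up more information.

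**What to change.** In section 11.2, pre-specify Cox models for PFS and for OS, fitted one covariate at a time and labelled exploratory, with age, number of lesions and total ablated diameter as continuous terms. Report hazard ratios with confidence intervals, and state how linearity will be checked. Keep the Kaplan-Meier curves at 5 lesions and 10 cm for display only; the sufficiency condition then governs only whether a curve is drawn. Because OS is dated from diagnosis of metastatic disease while lesion count and diameter are measured later, the OS model should also state its time origin or delayed entry; the planned log-rank strata raise the same question.

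The cost is a few lines of plan text and SAS code. Age follows from the date of birth collected under section 4.1. Sizes are needed for every ablated lesion, as the 10 cm cut already requires, so the form that records them should be confirmed. The downsides are a linearity assumption that a small number of events can check only roughly, and six exploratory tests (three covariates, two outcomes) without multiplicity control. Sample size, trial conduct and the primary test do not change.

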5.5 Evaluation for Severity of Pain and Quality of Life

Patients will be evaluated for severity of pain using the BPI-Short Form (Appendix B) with the assistance of a study coordinator at the following time points:

- Prior to ablation
- 1 day post-ablation
- 1 month post-ablation – from first procedure if more than 1 is done
- Time of disease progression

The patients are asked to answer the questions with respect to the lesion(s) treated. They are not given a copy of the BPI-Short Form and no prior responses are available to review on subsequent visits to minimize bias. Analgesic use following the tumor ablation will be recorded as well.

Patients will be evaluated on quality of life based on the FACT-G7 survey (Appendix C) with the assistance of the study coordinator at the following time points:

- Prior to ablation
- 1 day post-ablation
- 1 month post-ablation – from first procedure if more than 1 done
- Time of disease progression

They are not given a copy of the FACT-G7 form and no prior responses are available to review on subsequent visits to minimize bias.

These surveys may be administered over the phone.

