7.0 STUDY CALENDAR

Baseline evaluations are to be conducted within 3 weeks prior to start of protocol therapy. Scans and x-rays must be done no more than 3 weeks prior to the start of ablation.

	Baseline	Ablation	1 day after ablation	1 month after ablation	Follow-up ^d	Progression
Physical exam, incl. medical history, weight, VS, PS	X					
CBC	X					
CMP	X					
PT/PTT and INR	X					
Pregnancy test ^a	X					
IR evaluation ^b	X					
CT or PET scan					X ^d	
FACT-G7	X		X	X		X
BPI short form	X		X	X		X
Adverse events		X ^c				
Survival follow-up						X ^e

a: Women of childbearing potential only

b: Patients must have 10 or fewer treatable lesions when enrolled in the study and will be seen in consultation by an experienced interventional oncologic radiologist with evaluation of available PET, CT, MR, and US images for eligibility and lesion accessibility

c: Tracked for 30 days following ablation

d: The patients will be imaged as per routine care at the following time points: 6 weeks post first-procedure, every 9 weeks for the first year, every 12 weeks for the second year, and every 6 months for 5 years or until death or radiographic progression, whichever comes first.

e. After progression, patients will be followed every 3 months for survival only.

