8.0 DATA SUBMISSION SCHEDULE

Case report forms with appropriate source documentation will be completed according to the schedule listed in this section.

Case Report Form	Submission Schedule
Original Consent Form	Prior to registration
Registration Form Eligibility Form On-Study Form	Prior to starting treatment
Ablation Form	After treatment
Toxicity Form	30 days following ablation
Tumor Measurement Form Follow Up Form	Baseline 6 weeks after ablation Every 9 weeks during Year 1 Every 12 weeks during Year 2 Every 6 months for all subsequent years for 5 years or until progression or death Every 3 months after progression (survival only)
QOL Form	Baseline 1 day after ablation 1 month after ablation Progression

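### The GEE treats the survey at progression, which only progressors complete, as a fourth time point, so the three contrasts involving it mix within-patient change with who progressed

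*Combined protocol and SAP*

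**What the plan says.** Section 11.2 states that the QOL variables "will be measured at baseline, one day post ablation, one month post ablation and at time of disease progression". For the model, "the GEE analysis implemented in SAS PROC GENMOD will be used to take into account the correlation of repeated measures from the same subject". For the comparisons, "Contrast statements will be used to compare mean QOL scores between any two times". For pain, "The same analysis strategy will be performed to determine if BPI changes over time".

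The rest of the protocol agrees on the schedule. Section 5.5 ends the survey list for both instruments with "Time of disease progression". After baseline, the QOL form in Section 8.0 is due at "1 day after ablation 1 month after ablation Progression". No survey is planned at any fixed time after 1 month.

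Progression is found on imaging scheduled, in the Section 7.0 footnote, at "6 weeks post first-procedure, every 9 weeks for the first year, every 12 weeks for the second year, and every 6 months for 5 years". The same section adds: "After progression, patients will be followed every 3 months for survival only".

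Section 11.2 does not restrict the progression contrasts to progressors, bring in time to progression, name a working correlation, or say how the absent fourth score of a non-progressor is handled. Section 5.9 has certain patients counted as progressed, taken off trial and replaced. It does not say whether their survey data stay in the analysis.

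**The concern.** Baseline, 1 day and 1 month are occasions that every ablated patient is meant to have. The progression survey is different in kind, because the event itself creates it. A patient who does not progress has no fourth score and no late score to stand in for it, so the gap is not ordinary missing data. Progressors give their fourth score at very different times after ablation.

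A marginal contrast of progression against an earlier occasion sets a mean over progressors against a mean that also contains non-progressors. If patients who progress already had worse QOL or more pain at baseline, the contrast can show deterioration at progression when no patient changed. QOL and pain are two of the three secondary objectives in Section 2.2. The trial has one arm, so no control group would reveal the artefact.

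**Working it through.** **Scale.** The documents give no figure on this point. The only design figure is the sample size in Section 11.1, which reproduces: [(1.96 x sqrt(0.2 x 0.8) + 0.842 x sqrt(0.4 x 0.6)) / 0.2]^2 = 35.8, so n = 36.

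**Contrasts affected.** Four occasions give 6 pairs, of which 3 include progression. The count is the same for FACT-G7 and BPI.

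**Share with a progression score.** The 3-month PFS hypotheses of 20% and 40% in Section 11.1 imply 36 x 0.8 = 28.8 or 36 x 0.6 = 21.6 progressors by 3 months, if every failure is a progression. At that point about 7 to 14 patients contribute to the first three means only. Longer follow-up raises the share; unanswered surveys lower it.

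**Assumptions, not in the documents.** Outcome SD is 1 within progression status, scored so that lower is worse. Within-patient correlation is r = 0.6. No patient truly changes. Progressors are d = 0.5 SD worse at every occasion. A fraction f contributes a progression score.

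**Independence working correlation.** With time as a categorical factor, the contrast is the progressors' fourth mean minus the baseline mean of all patients. Its expectation is the true change among progressors minus (1 - f) x d. With no true change:

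- f = 0.6: -0.4 x 0.5 = -0.20 SD
- f = 0.8: -0.2 x 0.5 = -0.10 SD
- f = 0.9: -0.1 x 0.5 = -0.05 SD

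The large-sample variance is (1 + f^2 - 2fr)/(nf) + (1 - f)/n + d^2 f(1 - f)/n.

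- f = 0.6: 0.0296 + 0.0111 + 0.0017 = 0.0424; SE 0.206; ratio 0.97; rejection about 16%
- f = 0.8: 0.0236 + 0.0056 + 0.0011 = 0.0303; SE 0.174; ratio 0.57; rejection about 9%
- f = 0.9: 0.0225 + 0.0028 + 0.0006 = 0.0259; SE 0.161; ratio 0.31; rejection about 6%

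Rejection here is P(Z < -1.96 + ratio) + P(Z < -1.96 - ratio). Simulation of the same settings gives 15-17%, 8-10% and 6-8%.

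**Exchangeable working correlation.** The model now adjusts the fourth mean for how far progressors lay from everyone else on the first three occasions. The adjustment coefficient is k = 3a/(1 + 2a), where a is the marginal correlation, a = (0.6 + f(1 - f)d^2)/(1 + f(1 - f)d^2). The remaining bias is -(1 - f) x d x (1 - k).

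- f = 0.6: a = 0.66/1.06 = 0.623; k = 0.832; bias -0.20 x 0.168 = -0.03 SD
- f = 0.8: a = 0.64/1.04 = 0.615; k = 0.828; bias -0.10 x 0.172 = -0.02 SD
- f = 0.9: a = 0.6225/1.0225 = 0.609; k = 0.824; bias -0.05 x 0.176 = -0.01 SD

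Simulation gives about -0.01 to -0.04 SD and 6-8% rejection.

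**Paired analysis.** The progression-minus-baseline difference within progressors cancels each patient's own level. Its expectation is zero here whatever f and d are, and in simulation it rejects at about 5%.

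**The case against.** The strongest reply concerns size.

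- **High progression.** With 60-80% expected to fail by 3 months and imaging for up to 5 years, most patients may eventually progress. As an illustration, a constant hazard from 40% progression-free at 3 months leaves 0.4^2 = 16% at 6 months and 0.4^4 = 3% at 12. The share could then reach 90% or more, where the bias is about -0.05 SD even under independence. This stands, unless many patients die first or do not answer; the documents give no rate for either.
- **Working correlation.** A reader might infer that the plan commits to an analysis with 15-17% false positives. It does not. Section 11.2 neither states nor excludes an exchangeable structure, and under one the excess rejection nearly disappears.
- **Assumed gap.** Nothing in the documents gives a QOL or pain difference between eventual progressors and others. The 0.5 SD is illustrative.
- **Scope.** A reader might infer that the whole QOL analysis is compromised. The contrasts of baseline with 1 day and 1 month, which bear most directly on the effect of ablation, are not directly affected. In the assumed direction the artefact is a false worsening, not a false benefit, and no decision rule uses it.
- **Small samples.** A reader might also infer that the robust tests exceed 5% even without selection. That holds for a Wald z-test (6-7% in simulation), but Section 11.2 does not specify one, and a score-type contrast gave about 5%. The claim is not established.

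None of this gives the progression contrast a clear meaning. Even if every patient progressed, the visit would pool times from weeks to years and would not estimate change at any stated time.

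**Conclusion.** The point holds for three of six contrasts per instrument. As written, they combine change within patients with the make-up of the progressor group, and Section 11.2 contains nothing that separates the two.

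The numerical consequence is uncertain and may be small. Under the stated assumptions it runs from about -0.20 SD (independence, 60% contributing) to about -0.01 SD (exchangeable, 90% contributing). It is zero if progressors and non-progressors do not differ. These are secondary outcomes in a single-arm phase II trial and the primary endpoint is untouched. The change is still worth making, because the result depends on a modelling choice that the plan leaves open and the remedy costs very little.

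**What to change.** In Section 11.2, limit the GEE contrasts for FACT-G7 and BPI to baseline, 1 day and 1 month. Analyse the progression survey separately, as the paired within-patient change from baseline among progressors, and report the number of patients contributing and their time to progression.

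The cost is a few sentences of SAP text and slightly different SAS code, on the same data. The downside is that the progression result then applies to progressors only and says nothing about patients who did not progress.

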2.2 Secondary Objectives

1. To determine the rate of overall survival of patients with metastatic sarcoma stable on chemotherapy whose lesions have undergone ablation. Overall survival is defined as the time from diagnosis of metastatic disease to the time of death.
2. To determine the effects of ablation on quality of life (QOL) as measured with the FACT-G7 validated survey.
3. To determine the effects of ablation on pain as measured by the Brief Pain Inventory (BPI)-Short form, a validated scale for assessment of pain.

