5.0 TREATMENT PLAN

Eligible patients will have their lesions ablated using any one or more of the procedures described below. The choice of the procedure will be based on the expertise of the interventional oncologic radiologist and the site of metastasis. These techniques are thought to be equivalent.

Pre-and post procedure, patients must fill out a QOL survey and Brief Pain Inventory (BPI)-Short form, which is a validated visual analog scale for assessment of patient pain asking the patient to rate his/her worst pain in 24 hours. These surveys can be done over the phone.

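### Section 11.2 allows six unadjusted time contrasts each for QOL and pain, with no main contrast or analysed score: about a 20% chance of a spurious difference per instrument

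*Combined protocol and SAP*

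**What the plan says.** Secondary objectives 2 and 3 (section 2.2) concern the effects of ablation on QOL, "as measured with the FACT-G7 validated survey", and on pain, by the BPI Short Form. Section 11.2 says that QOL "will be measured at baseline, one day post ablation, one month post ablation and at time of disease progression" and that a GEE model will handle the repeated measures. It continues: "Contrast statements will be used to compare mean QOL scores between any two times". For pain: "The same analysis strategy will be performed to determine if BPI changes over time". The general rule is "All analyses will be two-sided at a significance level of 0.05".

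The two questions differ. For QOL, section 11.2 asks whether there is an improvement. For the BPI it asks only whether the score changes.

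Section 11.2 does not define the analysed score. It gives its reason for GEE as "since the variables related to QOL are in ordinal scale", in the plural, and then refers to mean scores. FACT-G7 (Appendix C) has seven items scored 0-4. Four rise as the patient gets worse (GP1, GP4, GP2, GE6) and three rise as the patient gets better (GF5, GF3, GF7). No total or reversal rule is given. Section 5.0 describes the BPI as "asking the patient to rate his/her worst pain in 24 hours", but section 11.2 does not make that item the analysed score.

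**The concern.** Four times give six pairwise comparisons per instrument, each at the full 0.05. The plan does not say which one answers the objective, so a significant result anywhere among the six could be put forward as the finding, at several times the error rate of a single test.

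The contrasts are also not interchangeable. At day 1 the BPI worst-pain item looks back 24 hours, onto the procedure or its immediate aftermath. A fall from day 1 to 1 month can therefore be recovery from the procedure. FACT-G7 looks back seven days, so its day-1 score mostly describes the days before ablation. The progression assessment (sections 5.5 and 7.0) exists only for patients who progress, so the three contrasts that use it rest on a selected group. Adjusting p-values cures none of this. Only naming the contrast does.

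What is at stake is how the QOL and pain results may be worded.

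**Working it through.** **The plan's own figure.** The plan states no error rate or power for QOL or pain. Its one calculation (section 11.1: 20% versus 40%, two-sided 0.05, 36 patients, at least 80% power) reproduces:

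N = [(1.960·√(0.2·0.8) + 0.842·√(0.4·0.6)) / 0.2]² = 5.98² = 35.8, rounded up to 36; power at 36 is 80.2%.

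I use it only to fix n = 36.

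**Inputs.** Four times, any pair, two-sided 0.05 (section 11.2). The documents give no within-patient correlation, so these are assumed: compound symmetry 0 to 0.8, first-order autoregressive 0.3 to 0.9, and a random walk. Every case has no true change at any time and one score per instrument.

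**Number of contrasts.** 4·3/2 = 6 per instrument, of which 3 are against baseline.

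**Any significant difference, either direction.** Six independent tests would give 1 − 0.95⁶ = 26.5%, but these six share four means. Under compound symmetry, at least one |z| > 1.96 is the event that the studentized range of four means exceeds 1.96·√2 = 2.77, which has probability 20.3%. The other rows and columns below are simulated (1,000,000 draws; 20,000 trials for GEE).

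| Setting | Any difference, 6 contrasts | Improvement, 6 contrasts | Improvement over baseline, 3 contrasts |
|---|---|---|---|
| Single contrast, nominal | 5% | 2.5% | 2.5% |
| Compound symmetry | 20.3% | 11.6% | 6.2-6.3% |
| Autoregressive 0.3 to 0.9 | 20.1-18.6% | 11.0-9.6% | 6.1-5.5% |
| Random walk | 18.2% | 9.3% | 5.3% |
| GEE, robust z tests, n = 36 | 24.3-24.9% | 13.8-14.4% | 7.8-8.2% |

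Improvement means that a later time is significantly better than an earlier one. The GEE row uses correlation 0.3 or 0.6, with the progression form observed in 60% or 100% of patients. Paired t tests at n = 36 (correlation 0.3-0.7) gave 20-21% and 11-12% for the first two columns.

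**Small-sample part of the GEE row.** Not all of that row is multiplicity. With 36 complete pairs, the uncorrected robust z equals the paired t times √(36/35). One contrast then rejects when |t| > 1.96·√(35/36) = 1.933 on 35 degrees of freedom, which is 6.1%.

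**Item-level testing (assumed; the plan neither states nor excludes it).** The chance of any difference would be about 39-50% for the four 0-10 ratings visible in Appendix B (inter-item correlation 0.8-0.6) and 61-73% for seven FACT-G7 items (0.6-0.4). These correlations have no source in the documents, and the copy of Appendix B that was read may lack a page.

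**Recovery from the procedure (size assumed).** Suppose pain rises by d SD on day 1 only. The day-1 to 1-month test then has mean z = d·√36 / √(2(1 − ρ)):
- d = 0.25: 1.27 at ρ = 0.3 and 1.94 at ρ = 0.7. Simulated chance of a significant fall: 22-48%.
- d = 0.5: 2.54 and 3.87. Simulated chance: 69-96%.

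In the same simulations, significant improvement over baseline stayed near 5%.

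**The case against.** The best defence is that these are secondary objectives in a single-arm phase II trial, where unadjusted contrasts are common and the primary test is untouched. That limits the consequence. But the plan does not label these analyses exploratory, and it applies 0.05 to all analyses.

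A reader might infer three stronger points, which the documents do not support:

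- **That an improvement will be found by chance about 20% of the time or more.** The 20% counts worsening as well as improvement, and it falls to 18% under serial correlation, so it is not a floor. Improvement is also the stated question for QOL only.
- **That any single significant contrast counts as proof of improvement.** Section 11.2 contains no such rule. It is silent on which contrast decides.
- **That the item-level rates are the plan's error rates.** They describe testing that the plan does not specify.

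Two cautions also stand. Section 5.5 asks patients to answer the BPI with respect to the treated lesions, and the documents give no data on day-1 pain, so the recovery effect is possible but not shown. The 1-month form is timed from the first procedure, which weakens the recommended contrast for patients who have several procedures.

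**Conclusion.** The concern holds for the contrasts and the undefined score. Each instrument has six unadjusted contrasts, with neither a main contrast nor an analysed score designated in section 11.2. On one score with no true change:

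- A spurious difference of either sign has about a 20% chance (18-25%), roughly four times the 5% of one test. This is the relevant figure for the BPI question.
- A spurious improvement has about a 9-14% chance over all pairs, or 5-8% against baseline only, compared with 2.5%. This is the relevant figure for the QOL question.

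These rates rest on assumed correlation structures and on all six contrasts being run. Fewer contrasts would lower them, and testing items singly would raise them. The effect is confined to what may be claimed about QOL and pain; the 3-month progression-free rate is unaffected.

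**What to change.** In section 11.2, name one score and one contrast per instrument, each tested two-sided at 0.05:

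- **QOL:** FACT-G7 total, with GP1, GP4, GP2 and GE6 reverse-scored so that higher is better; baseline versus 1 month.
- **Pain:** BPI worst pain in the last 24 hours, the item that section 5.0 already singles out; baseline versus 1 month.

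Report all other contrasts and items as estimates with 95% CIs, labelled exploratory. If all six contrasts must stay confirmatory, each needs p < 0.05/6 = 0.0083 (Bonferroni) or |z| > 2.57 (Tukey), but that does not deal with recovery from the procedure or with the selected progression group.

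State also that the 1-month form is timed from the first procedure (section 5.5). The schema allows ablation to run over 3 weeks, so taking a month as 30 days, the form may fall only 30 − 21 = 9 days after the last procedure.

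The cost is a few sentences. Both times are already collected for both instruments (sections 5.5 and 7.0). The downside is that the other contrasts can no longer support a claim.
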